8.2 Study Populations

Individuals from populations who are under-represented in clinical research (e.g., racial and ethnic minorities, women, individuals from rural/frontier communities, older individuals) will be enrolled with a goal of ensuring that all eligible patients are given the opportunity to participate in novel clinical trials and that research findings can be generalizable to the entire population.

Pregnant women, those who lack consent capacity, the mentally ill, prisoners, cognitively impaired persons, children, and employees will not be included in this research study.

8.3 Lifestyle Considerations

During this study, subjects are asked to:

- Refrain from consumption of any food, beverages, gum, saliva substitutes, or smoking for 1 hour prior to each salivary collection. Patients will be called the day prior to study visits to remind them about these restrictions.

8.4 Subject Identification

Identification in Clinical Practice

Potential subjects may be identified during routine visits to Radiation Oncology and Otolaryngology clinics. A member of the clinical team will inform potential subjects of the research opportunity and explain the study. Potential subjects will be pre-screened through medical record review. Information collected from potential subjects who are not enrolled will be destroyed. Potential subjects who meet all pre-screening criteria will be invited for a formal consent and baseline visit. If the potential subject is interested in learning more, an IRB approved consent will be provided and discussed with the potential subject.

Self Identification

Potential subjects may self-identify as potential subjects after reading online information about the study (clinical trials.gov). Potential subjects who self-identified and contact the UWCCC be referred to a member of the clinical trials team. The clinical team member will further discuss the research opportunity and complete a pre-screening. Potential subjects who meet all pre-screening criteria will be invited for a formal consent and baseline visit. If the potential subject is interested in learning more, an IRB approved consent will be provided and discussed with the potential subject.

Electronic Medical Record Query

Potential subjects may also be identified via EMR query using diagnostic codes for head and neck cancer and radiation therapy and other eligibility criteria. The research team will conduct further prescreening of individual records to further refine the list of potential subjects.

Department Database

The head and neck cancer database (HS IRB #2015-1216), described under a separate protocol may be used to identify eligible subjects.

8.5 Subject Recruitment

A total of 6 subjects with bilateral submandibular glands for unilateral gland injection will be recruited from UW-Madison. Potential subjects will be recruited from clinical practice at UWCCC. If the potential subject is agreeable, they will be provided contact information for the study team or the research team will initiate contact.

8.6 Remuneration and Retention Strategies

Many visits will occur in concert with standard of care followup visits for patients. Patients will be contacted 2 weeks prior to each visit to be reminded of the upcoming appointment and the next appointment will be made before the patient leaves the clinic.

8.7 Early Termination and Withdrawal

Subjects are free to withdraw from participation in the study at any time upon request.

The Principal Investigator (PI) may discontinue or withdraw a subject from the study for the following reasons at his/her discretion:

- Pregnancy
- Subject non-compliance with study requirements (e.g., study intervention non-compliance)
- If any clinical adverse event (AE), laboratory abnormality, or other medical condition or situation occurs such that continued participation in the study would not be in the best interest of the subject
- If the subject is no longer an appropriate candidate for participation
- There is evidence of progressive disease or unacceptable toxicity
- Subject unable to receive MSC injection, either due to subject choice or investigator decision based on MSC release guidelines

Subjects who sign the informed consent form but do not receive the the MSC injections will be replaced. Subjects who sign the informed consent form and receive the the MSC injections, then subsequently withdraw, or are withdrawn or discontinued from the study, will not be replaced.

The following actions will be taken if a subject withdraws, or fails to return for a required study visit:

- The site will attempt to contact the subject and reschedule the missed visit within 2 weeks and counsel the subject on the importance of maintaining the assigned visit schedule and ascertain if the subject wishes to and/or should continue in the study.
- Before a subject is deemed lost to follow-up, the investigator or designee will make every effort to regain contact with the subject where possible, 3 telephone calls and, if necessary, a certified letter to the subject's last known mailing address. These contact attempts shall be documented in the subject's study file.
- If the subject continues to be unreachable, they will be considered to be lost to follow-up.

If a subject is prematurely withdrawn from the study for any reason, the investigator will under all circumstances try to perform all evaluations described for the early termination visit

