13.5 Treatment and Study Compliance

The intervention in this study is a one-time injection that involves a procedure performed by study personnel so that there is limited concern with adherence to the intervention. The primary endpoint is based upon short-term outcomes and thus study compliance is expected to be good. Patients will be called by study coordinator to remind them of all study visits. Secondary endpoints are assessed up to 24 months after the intervention. To maximize study compliance, patients will receive regular reminders of study visits and all visits will be scheduled up to 1 year in advance.

The number of patients who complete each study visit and assessment will be provided in a CONSORT diagram at the time of publication.

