15.12 Follow-up of Adverse Events

Only grade 3 or 4 Adverse Events (AEs) that are thought to be at least possibly related to the study will be followed until the event has resolved or, in the case of a clinically significant abnormal laboratory value, it has returned to baseline or stabilized at an acceptable level according to the PI.

- There is a satisfactory explanation for the changes observed, or
- The patient is lost to follow-up or off study

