16.5 Study Stopping Rules

This study may be temporarily suspended or prematurely terminated if there is sufficient reasonable cause. If the study is prematurely terminated or suspended, the PI will promptly inform the IRB, FDA, and will provide the reason(s) for the termination or suspension.

Patient enrollment and treatment will be temporarily halted if the following rules occur, pending review by the UWCCC DSMC, and FDA if:

- Any death, irrespective of attribution by the investigator
- Any (CTCAE v5.0) of grade 4 or higher
- Any hypersensitivity reaction grade 3 or higher at any time
- Any grade 3 SAE in the first 3 subjects
- Any 2 grade 3 or higher of the same SAE at any time during the study
- 5 or more grade 3 or higher SAEs that are at least possibly related at any time during the study

Other circumstances that may warrant termination or suspension include, but are not limited to:

- Determination of unexpected, significant, or unacceptable risk to subjects
- Data that are not sufficiently complete and/or evaluable

If the study is suspended, it will not be reopened without prior FDA approval and without protocol modifications if recommended by the FDA or UWCCC DMSC. If the study is suspended, all subjects will still be followed as specified in the protocol.

Any change to the study stopping rules must first be reviewed by the FDA.

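### Sections 8.7 and 15.12 let a PI-initiated withdrawal after injection end scheduled follow-up, including of an unresolved related grade 3-4 event, with only one exit visit in between

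*Combined protocol and SAP*

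**What the plan says.** **Withdrawal.** Under 8.7 the PI "may discontinue or withdraw a subject from the study for the following reasons at his/her discretion". The list includes "There is evidence of progressive disease or unacceptable toxicity", "Subject non-compliance with study requirements (e.g., study intervention non-compliance", and an adverse event or other condition that makes staying in the study contrary to the subject's interest. Nothing confines these grounds to the period before injection. The same section expects withdrawals after injection, because it says that injected subjects who leave are not replaced.

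**Treatment.** Section 13.5 states: "The intervention in this study is a one-time injection that involves a procedure performed by study personnel". The only later treatment is the optional contralateral injection (7.1).

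**Follow-up of events.** Section 15.12 says: "Only grade 3 or 4 Adverse Events (AEs) that are thought to be at least possibly related to the study will be followed". Among the end points it lists: "The patient is lost to follow-up or off study".

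**Exit visit.** On premature withdrawal, 8.7 says "the investigator will under all circumstances try to perform all evaluations described for the early termination visit". Section 10.5 sets the content as the assessments of the 24-month visit and requires the reason for leaving to be documented.

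**Late events.** Section 15.8 keeps grade 3 or higher events that are at least possibly related reportable without a time limit. Section 16.4 requires expedited reports of serious events beyond 30 days when attribution is probable or definite.

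**Analysis.** Section 13.3 puts every injected patient in the safety set. Section 13.8 analyses the drop-out rate together with the reasons.

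**The concern.** Once a subject has been injected, there is little treatment left to stop. Applying an 8.7 ground at that point may cancel a possible second injection, but its main effect is to end observation. Because the grounds include toxicity and progression, the decision to stop observing can depend on the outcome being observed.

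The primary objective is safety, and 5.4 describes the product as first-in-human. Subjects enter with no evidence of disease, so progression is itself of safety interest. At stake are the course and duration of a related severe event, late related events, and saliva and QoL data out to 24 months in the subjects doing worst. The same applies after the contralateral injection, for which 7.1 plans safety visits to 24 months.

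**Working it through.** The plan gives no figure for this point. The check sets the sections side by side and then sizes one removal.

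**1. What remains after a PI withdrawal following injection**

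| Item | Source | After withdrawal |
|---|---|---|
| Triggering event | 15.8, 10.3 | Recorded |
| Place in safety denominator | 8.7, 13.3 | Kept; not replaced |
| Exit visit | 8.7, 10.5 | One, to be attempted |
| Blood count at that visit | 10.1, 10.3 | None (follow-up counts are at 1 and 3 months only) |
| Ultrasound at that visit | 10.1, 11.6 | None (follow-up scans are at 3, 6 and 12 months only) |
| Scheduled contact after that visit | None found | None |
| Unresolved related grade 3-4 event | 15.12 | Follow-up may end |
| Late related grade 3+ events and late serious events | 15.8, 16.4 | Reportable, but only if the site hears of them |

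Two details matter. Neutropenia and thrombocytopenia are on the toxicity list in 9.7, yet a subject removed for either would have no protocol blood count at the exit visit. In addition, the sub-study calendar's 24-month visit has only a physical examination and an AE assessment, without saliva or QoL. Section 10.5 does not say which 24-month schedule applies after a contralateral injection.

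**2. Two groups with explicit follow-up**

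Subjects withdrawn because their product could not be given are followed for 1 month after aspiration (9.1). For suspension of the whole study, 16.5 says: "If the study is suspended, all subjects will still be followed as specified in the protocol". No corresponding sentence covers an injected subject whom the PI withdraws.

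**3. Size of one removal**

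Planned follow-up is 730 days (10.1). The day of removal is an assumption. Share forgone = (730 − day)/730.

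- Day 40: 690/730 = 94.5%; the 3-, 6-, 12- and 24-month visits are forgone.
- Day 90, after that visit: 640/730 = 87.7%; the 6-, 12- and 24-month visits are forgone.
- Day 180, after that visit: 550/730 = 75.3%; the 12- and 24-month visits are forgone.
- Day 365, after that visit: 365/730 = 50.0%; the 24-month visit is forgone.

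In each case one attempted exit visit stands in for the visits forgone. One subject of six is 1/6 = 16.7%.

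**4. Effect on a late-event rate**

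The synopsis gives a 95% CI of 0-64% for 1 of 6. The exact (Clopper-Pearson) interval reproduces it:

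- Lower limit: 1 − 0.975^(1/6) = 0.4%.
- Upper limit: the p that solves (1−p)^6 + 6p(1−p)^5 = 0.025, which is 64.1%.

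If the only late event arose after removal and nobody reported it, the count would be 0 of 6. The upper limit would then be 1 − 0.025^(1/6) = 45.9%, with a lower limit of 0. This applies only to an event that first appears after the exit visit, since the triggering event is already recorded.

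**The case against.** The strongest reply is that the safeguards are substantial. Section 8.7 is permissive, and its adverse-event ground is tied to the subject's interest. The exit visit in the main study covers examination, saliva, QoL, adverse events and banked blood. Related severe events stay reportable, and every injected subject stays in the safety set. Withdrawal also spares a subject with progressive cancer further research procedures, and the list in 8.7 has to serve pre-injection cases as well. The wording of 15.12 is fragmentary: its bullets follow a complete sentence with no lead-in, so reading the off-study clause as an end point is the natural reading but not a certain one.

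Much of this stands, and it rules out several stronger inferences that a reader might draw:

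- **That harmed subjects vanish from the safety data.** They do not. The event and the denominator are kept; what can be lost is the later course.
- **That the DLT decision is compromised.** Sections 5.5 and 14.3 report no DLTs or serious events within one month, and day 40 is already the last day of the 1-month visit window (30 ± 10).
- **That 16.5 contradicts 8.7.** One concerns the whole study and the other a single subject. It is a contrast, not a conflict.
- **That PI removals distort the drop-out rate and should be left out of it.** Reasons are already collected (10.5) and analysed (13.8). Leaving out toxicity removals would hide information that matters for the next trial.

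What the reply does not answer is the period after the exit visit. Reporting duties without scheduled contact rely on someone telling the site.

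**Conclusion.** The point holds as a gap in follow-up rules. Followed as written, 8.7 and 15.12 allow outcome-dependent loss of scheduled follow-up after injection, and an unresolved related grade 3-4 event need not be followed once the subject is off study. One removal affects 16.7% of a six-subject cohort and forgoes between 50.0% and 94.5% of planned follow-up over the assumed removal dates from day 365 back to day 40.

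This rests on reading the off-study clause in 15.12 as an end point and on a removal actually taking place. The documents report no such removal and give no probability of one. The consequence is confined to follow-up out to 24 months and to the contralateral injections. It is an inexpensive improvement, not a flaw in the primary result.

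**What to change.** Reconcile 8.7, 10.5, 15.8 and 15.12 on data collection only:

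- State in 8.7 that an injected subject discontinued by the PI remains in the safety and outcome data collection already scheduled to 24 months, unless the subject withdraws consent or is lost to follow-up.
- Limit the off-study clause in 15.12 to those two cases, and give its bullets a lead-in sentence.
- Say in 10.5 which 24-month schedule defines the exit visit after a contralateral injection.
- Keep all post-injection exits in the drop-out rate, and tabulate PI-initiated and subject-initiated exits separately from the reasons already recorded.

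The PI's clinical grounds for withholding an injection stay as they are. The cost is a wording amendment, plus keeping visits that are already planned for the few subjects who would otherwise have been removed.

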9.0 STUDY TREATMENT

9.1 Description of the Investigational Medicinal Product (IMP)

Drug Substance:

Autologous bone marrow-derived MSCs at a concentration of 10×10^6 cells/mL

Drug Product (IMP):

Suspension of autologous bone marrow-derived MSCs suspended in a solution of Plasmalyte A containing 0.5% human serum albumin. Cells will be administered at one dose level, Dose 0, with a possible lower dose if the DLT criterion is reached. For each cell dosage we have set a 20% acceptable deviation. Dose levels and acceptable ranges (in parentheses) are as follows:

- Dose -1: $5 (4 - 6) \times 10^6$ MSCs (into one submandibular gland; to be used only if Dose level 0 is not tolerated)
- Dose 0: $10 (8 - 12) \times 10^6$ MSCs (into one submandibular gland)

If the MSC IMP is not administered to the patient due to a failure of the MSCs to expand to achieve the required dose/ or the MSC IMP does not pass QA testing, the subject will be withdrawn from study, and followed for 1 month post the aspiration procedure to ensure AE/SAEs are appropriately recorded. These subjects will be replaced in the study by the recruitment of another subject.

Route of administration: injection into one submandibular gland (must have 2 glands present). The gland selected will be the gland that received the lower radiation dose. The contralateral gland of each interested subject will be injected with autologous MSC IMP at Dose level 0 following completion of the primary objective with no DLTs reported.

9.2 Preparation of the IMP

Up to 30 cc of bone marrow will be aspirated from the posterior superior iliac crest of each subject under aseptic conditions and local anesthesia by a qualified UW medical personnel. The bone marrow aspirate will then be hand delivered to the UW PACT GMP Cell Manufacturing Facility. UW PACT staff member will document receipt of the bone marrow aspirate and commence the processing according to the standard operating procedure. Mononuclear cells (MNCs) will be isolated by using Ficoll-Paque PREMIUM 1.073 g/mL medium (GE Healthcare) and density gradient centrifugation. Cells will be washed in CTS™ DPBS (GIBCO®) and re-suspended in culture medium supplemented with Gentamicin, USP at 5 μ g/mL. The culture medium will consist of MSC NutriStem® XF Medium (Biological Industries), 5% PLTMax® human platelet lysate (Mill Creek Life Sciences), 1% CTS™ GlutaMAX™ I (GIBCO®), and Heparin Sodium, USP at 2 U/mL. The MNCs will then be placed into tissue culture flasks at 100,000 – 200,000 cells/cm² density. After 72 hours in 5% CO₂/37°C humidified incubator, culture medium will be aspirated, non-adherent cells will be washed off with CTS™ DPBS (GIBCO®). Adherent cells will be returned into the incubator with fresh culture medium for additional 4-7 days. MSCs will be harvested using CTS™ TrypLE™ Select Enzyme (GIBCO®) and re-seeded into tissue culture flasks at 3,000 cells/cm² density for further expansion. Cells will reach approximately 70% confluence after 3 days in culture. Additional passage may be necessary in order to generate clinically relevant number of MSCs. Once desired number of cells and confluence is achieved, MSCs will be subjected to cytokine licensing by replacing spent medium with fresh culture medium supplemented with recombinant human IFN-gamma GMP Protein (R&D

Systems) at 1200 IU/mL. One flask will receive no IFN-gamma and serve a negative control. MSCs will augment their immunomodulatory properties after 24 hours of exposure to IFN-gamma. Stimulated MSCs will be analyzed via flow cytometry for upregulation of PD-L1, MHC I, MHC II, IDO, and Icam markers, which are indicative of the immunosuppressive phenotype. In addition, cell identity will be confirmed using Miltenyi Biotec MSC Phenotyping Kit. MSCs will be expected to stain positive for CD73, CD90, CD105 and negative for CD14, CD19, CD34, CD45 markers. IFN-gamma stimulated MSCs will then be cryopreserved at 5,000 cells/mL in 20% Plasma-Lyte A (Baxter), 20% Human Serum Albumin (FLEXBUMIN, Shire), 10% dimethyl sulfoxid (CryoMACS® DMSO Miltenyi Biotec). Cryovials will be stored in a vapor phase of LN₂ storage dewar within UW PACT GMP Cell Manufacturing Facility. In preparation for injection, vials will be thawed using ThawSTAR automated cell thawing system (BioLife Solutions). Cells will be washed twice in the MSC culture medium and seeded into flasks at 25,000 cells/cm² for 16 hours of culture-rescue, at which point cells have been shown to fully restore their immunomodulatory properties. MSCs will be harvested and re-suspended at 10 x 10⁶ cells/mL in Plasma-Lyte A containing 0.5% human serum albumin. The suspension is then transferred into appropriately sized syringe. One milliliter of the suspension will be dispensed for the quality control testing. If the remaining volume in the syringe exceeds the pre-determined cell dose, the surplus will be allocated to the retention sample. The IMP will be released upon meeting the following specifications: viability >70%, endotoxin < 5 EU/mL, stat gram stain negative, dose level within 20% deviation of the target dose. Mycoplasma test results and 14 day sterility culture results will not be available on the day of injection.

9.3 Packaging, Labeling and Storage of the IMP

Packaging

The autologous bone marrow-derived IFN-gamma stimulated MSC product will be delivered in a 10 mL Becton Dickinson Luer-Lok™ Syringe(s) sterile, single use (Product Number 302995). This product is sourced from hospital inventory and deployed within the University of Wisconsin Hospital and Clinics.

Labeling

Labeling of IMP is compliant with FDA regulations and includes the patient's unique identifiers (medical record number, date of birth), product name, batch number, date and time of manufacture, expiration date and time, identification of the processing lab.

Storage

The IMP is intended for direct administration after preparation. The IMP containing autologous bone marrow-derived MSCs re-suspended at a concentration of 10x10⁶ cells/mL in a solution of Plasma-Lyte A containing 0.5% human serum albumin has been shown to maintain viability >70% for 24 hours at room temperature. However, to maintain highest viability the product will be injected as soon as clinically possible. Until injection, the IMP will be stored at room temperature.

Packaging, labeling and storage of the IMP will follow UW PACT SOPs developed and qualified according to cGMP standards.

9.4 Transport of IMP

The IMP will be transported from the GMP Cell Manufacturing Facility to the clinical site (ENT clinic) in a qualified temperature controlled cooler at 20-25°C according to the UW PACT SOP.

9.5 IMP Accountability

The PI is responsible for maintaining accurate accountability records throughout the study. The administration of the IMP will be documented in the patient's medical file in a procedure note.

9.6 Retention samples, if available, will be cryopreserved and stored in a vapor phase of LN₂ storage dewar within the GMP Cell Manufacturing Facility. Retention samples will be kept for a minimum of 2 years. Retention samples may then be discarded according to applicable regulations for disposal of biological products. The PACT GMP Cell Manufacturing facility has assessed each patient's MSC IMP to ensure the cryopreserved product is stable and appropriate for second injection (See Appendix 19.4 for stability data). The MSC IMP administered for the second injection will undergo the same quality control testing detailed in section 9.2 prior to injection. Administration of IMP

MSCs will be supplied in one single use 10 mL Becton Dickinson Luer-Lok™ Syringe sterile, single use (Product Number 302995) at the pre-specified dosage levels for each gland to be injected. No preparation is required. Administration by [name] will occur as follows:

- Subjects will be placed in a semi-recumbent position
- Injection of 2mL of 1% lidocaine with 1:100,000 epinephrine into the submandibular gland area.
- Visually inspect the syringe for particulate matter and/or discoloration prior to administration. If either of these conditions exist, do not administer
- Gently shake the prefilled syringe
- Identify each submandibular gland with US and cleanse the injection site with chlorhexidine.
- Insert 22 G x 1 ½" needle (Becton Dickinson's Precisionglide™ hypodermic needle [Product Number 305194]) at a 90-degree angle to the skin and inject all of the contents of 1 syringe into a submandibular gland under US guidance at a rate of ≤2 mL/min. This rate and needle gauge was chosen in part, due to the work published by Mamidi and colleagues, demonstrating that repeatedly passing mesenchymal stem cells (MSC) through substantially smaller gauge needles (24, 25, and 26G) has no impact on MSC morphology, attachment, viability, phenotype, differentiation potential, and in vivo migration abilities³⁰. Do not inject the IMP subcutaneously or intravenously. Care should be taken to avoid administering the injection into or near blood vessels and nerves.
 - Ultrasound guidance will be used to 1) ensure intraglandular (sub-capsular) injection into the submandibular gland and, 2) avoid intravascular injection into branches of facial and lingual vessels.
- Monitor the subject for at least 30 minutes post administration.

